8.7.2.1.3 Tipping Point

A tipping point analysis of the primary endpoints will be performed as a sensitivity analysis for the handling of missing data. The multiple imputation datasets used for the primary analyses will be used for the tipping point analyses for lesion counts. To perform the tipping point analysis, the imputed values from the multiple imputation datasets for only the E-BPO/E-ATRA cream arm will be adjusted, by adding a constant (shift value) to the lesion counts. Change from Baseline will then be recalculated with the changed imputed values. The shifted multiple imputed datasets will then be analyzed as described in the primary endpoint section. This will then be repeated by adding the constant again to create another new shifted multiple imputed dataset and that dataset will be analyzed. The resulting point estimates and p-values associated with each shift value will be presented in order to assess the magnitude of the shift value required to “tip” the p-value greater than 0.05.

8.7.2.2 Sensitivity Analyses for IGA

8.7.2.2.1 Repeated Measures

The first sensitivity analysis for the dichotomized IGA success will use a repeated measures logistic regression model (generalized estimating equations), with dichotomized IGA success as the dependent variable and treatment, analysis center, visit (i.e., Week 2, Week 4 and Week 8), and treatment group by visit interaction as independent factors. In this analysis, data from all post-baseline visits will be included with no imputation for missing data.

8.7.2.2.2 Model Based Multiple Imputation

The second sensitivity analysis will use the model based multiple imputation method to impute missing data for the dichotomized IGA data. The multiple imputation will involve 3 principal tasks:

1. Missing values will be filled in 5 times to generate 5 complete data sets. The imputation model used logistic regression with factors of treatment group and analysis center (i.e., the imputation model will be the same as the analysis model).

Syntax:

```
proc mi data=datain out=dataout seed=&seed. nimpute=5 <options>;  
  class trtpn sitegr1 diiga;  
  var trtpn sitegr1 diiga;  
  monotone logistic (sitegr1=trtpn);  
  monotone logistic (diiga=trtpn sitegr1);  
run;
```

2. Each complete data set will be analyzed with a logistic regression a factors of treatment group and analysis center.
3. Results from these analyses will be combined into a single inference.

One random seed will be needed to impute IGA. The following random seed has been pre-specified by using a random number generator:

IGA Seed= 1857263794

8.7.2.2.3 Tipping Point

A tipping point analysis of the primary endpoint will be performed as a sensitivity analysis for the handling of missing data. To perform the tipping point analysis for the dichotomized IGA, all combinations for the number of imputed successes for the nonrespondents in the E-BPO/E-ATRA cream group and the vehicle group will be analyzed to identify the points that would indicate a treatment failure using a p-value greater than 0.05. The resulting points of treatment failure will be plotted with the average number of successes in each treatment group from the primary multiple imputation analysis overlaid. The tipping points of the study will be identified by the points where the particular combinations of imputed successes that change the treatment success to a treatment failure.

8.7.3 Secondary Efficacy Analysis

Appropriate descriptive statistics will be computed for all secondary efficacy parameters.

Additionally, all inferential testing of percent change in lesions will follow the methods for the primary lesion count analyses. Methods corresponding to the analysis of IGA will be used to compare the proportion of patients in the E-BPO/EATRA Cream arm versus vehicle control achieving at least a 4-point reduction in pimples (item1 of the PRE-FACE) or in embarrassment (item5 of the PRE-FACE) scores from Baseline to Week 12.

A stepwise process will be conducted for testing the secondary efficacy endpoints in order to control for multiplicity, refer to Section 8.1.8.

The secondary efficacy analysis will be presented on the ITT and PP populations.

8.7.4 Supportive Efficacy Analysis

Appropriate descriptive statistics will be computed for all supportive efficacy parameters.

Additionally, all inferential testing will follow the methods for the co-primary variables wherein the continuous variables will parallel the lesion count analyses and the discrete dichotomized variables will follow the analysis of the IGA. Inferential testing for PGI-S and PGI-TS at Week 12 will use a cumulative logistic regression with factors of treatment group and analysis center. Missing values will not be imputed.

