	
6. Visit 6/Week 12, Day 85 (\pm 4 Days)/ End of Study or Early Termination.
 
Patients will be admitted into the study after written informed consent has been obtained, and all inclusion/exclusion criteria have been met, including a clinical diagnosis of acne vulgaris. Patients with severe acne vulgaris who are appropriate for systemic treatment need to be counseled regarding their treatment options by the Principal Investigator.
 
Prior to any treatment related assessments, questionnaires are to be completed by all patients, starting the age of 9 years old:
 
 1. Patient reported outcomes (PRO) will be assessed with the Patient-Reported Evaluation of Facial Acne (PRE-FACE) and the Patient Global Impression of Symptom Severity (PGI-S) at: Screening, Baseline, Weeks 2, 4, 8, and 12/ Early Termination. The Patient Global Impression of Change (PGI-C), Patient Global Impression of treatment Side Effects (PGI-SE), and Patient Global Impression of Treatment Satisfaction (PGI-TS) will be assessed at: Weeks 2, 4, 8, and 12/ End of Study or Early Termination. 2. Acne Quality of Life (QoL) questionnaire at Baseline and week 12/ End of Study or Early Termination 
At each visit, a 5-point scale Investigator Global Assessment (IGA) ranging from 0 (Clear) to 4 (Severe) of acne assessment and facial lesion counts (inflammatory and non-inflammatory) will be performed. Investigators will be provided with instructions for IGA assessments and lesion counts to ensure consistency of procedures.
 
Safety will be assessed at all visits and will include monitoring of adverse experiences; the Investigator Cutaneous Safety Assessment rating of pigmentation, erythema, dryness and scaling on a scale ranging from 0 (None) to 3 (Severe); and the Patient assessment of Local Tolerability rating itching burning and stinging on a scale ranging from 0 (None) to 3 (Severe). Urine pregnancy tests will be performed for all females of child-bearing potential and premenarchal females, at every visit: Screening, Baseline, Weeks 2, 4, 8 and 12/ End of Study or Early Termination.
 
Standardized optional photography of the face at Baseline and all study visits will be performed at select sites.
 
Regardless of the duration of the study, all patients that exhibit serious adverse event (SAE), will be followed up until the SAE stabilizes or resolves, based on Investigator’s medical judgment.

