12.10 Study Flow Chart

Procedures	Visit 1 ¹	Visit 2 ²	Visit 3 ²	Visit 4 ²	Visit 5 ²	Visit 6 ³ (EOS ⁴ / ET ⁵)
Name of Visit	Screening	Baseline Day 1	Week 2 Day 15	Week 4 Day 29	Week 8 Day 57	Week 12 Day 85
Visit Window	Day -35 to Day 0		±3 days	±3 days	±3 days	±4 days
Informed Consent/Assent	X					
Demographics	X					
Medical History/ Previous Therapies	X	X				
Brief Physical Examination & Vital signs		X				X
Inclusion/Exclusion Criteria	X	X				
Urine Pregnancy Test ⁶	X	X ⁷	X	X	X	X
Complete PRE-FACE and PGI-S ⁸	X	X	X	X	X	X
Complete PGI-C, PGI-TS and PGI-SE ⁹			X	X	X	X
Complete Acne-QoL questionnaire ¹⁰		X				X
IGA	X	X	X	X	X	X
Lesion Counts	X	X	X	X	X	X
Assessment of Eligibility		X				
Randomization		X				
Cutaneous Safety Assessment and Local Tolerability Assessments		X	X	X	X	X
Administer/ Review Patient Instructions		X	X	X	X	
Weigh Study Product		X		X	X	X
Dispense Study Product		X ¹¹		X	X	
Dispense Cleanser & Moisturizer		X ¹²				
Diary Card dispensed		X		X	X	
Study Product collected				X	X	X
Diary Card collected				X	X	X
Patient Compliance Reviewed (Diary)			X	X	X	X
Prior and Concomitant Therapy and Medication Reviewed	X	X	X	X	X	X
Assessment of Adverse Events	X ¹³	X	X	X	X	X
Photography (select site(s))		X	X	X	X	X

¹ If no washout is needed, Visits 1 and 2 may occur on the same day. If a washout is needed, visit 2 must occur within 35 days of Visit 1.

² All visit dates are in reference to Baseline, e.g., Visit 5 occurs 8 weeks ± 3 days after Baseline Visit.

³ Week 12/ End of Study procedures should be completed for Patients who terminate early.

⁴ EOS – End of Study

⁵ ET – Early Termination

⁶ All females of child-bearing potential and premenarchal must undergo Urine Pregnancy Tests, at every visit.

⁷ Urine Pregnancy test should be repeated if more than 2 weeks washout is needed.

⁸ Questionnaires are to be completed by all patients prior to any treatment related assessments. In case Screening Visit and Baseline occur at the same day, the PRO questionnaires should be completed prior to screening procedures.

⁹ Questionnaires are to be completed by all patients prior to any treatment related assessments.

¹⁰ Questionnaires are to be completed by all patients prior to any treatment related assessments. In case Screening Visit and Baseline occur at the same day, the QoL questionnaires should be completed prior to screening procedures.

¹¹ Dispense one pump of study product at the Baseline Visit and dispense additional pump at Visit 4 and 5.

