Patient Global Impression of symptom Severity (PGI-S): The PGI-S (presented in appendix 4) is a single-item global self-assessment of the current severity of Patients’ acne vulgaris symptoms rated on a five-point verbal response scale ranging from 0 (None: No pimples, clear skin) to 4 (Very severe: Large amount of pimples, no clear skin), where higher scores indicate greater severity of acne vulgaris symptoms. The PGI-S will be administered at study visits 2-6, including Screening, Baseline, and at Weeks 2, 4, 8, and 12/ End of Study or Early Termination. While PGI-S results can inform treatment efficacy, a main use for the tool in this study is to support supplementary anchor-based analysis. Anchor-based analysis use an external criterion (in this case, the PGI-S) to categorize Patients into groups each reflecting an *a priori* determined change grouping (e.g., no change, large positive change, or large negative change) to inform conclusions about the meaning of observed within person change on other measures.

Patient Global Impression of Change (PGI-C): The PGI-C is a single item questionnaire that asks respondents to describe the change they have noticed in their acne symptoms since the start of the study on a 7-point VRS ranging from “Very much improved” to “Very much worse”. Patients are encouraged to look in a mirror to help with their response and the questionnaire can be completed in less than 30 seconds. The PGI-C is administered via pen-and-paper at the site visits at Week 2, Week 4, Week 8 and Week 12/ End of Study or Early Termination. Similar to the PGI-S described above, the PGI-C data collected in this study to support supplementary anchor-based analysis.

Patient Global Impression of Treatment Satisfaction (PGI-TS): The PGI-TS is a single item questionnaire that asks respondents to describe how satisfied they are “right now” with the acne treatment administered as part of the study on a 5-point VRS ranging from “I am very satisfied” to “I am very dissatisfied”. The questionnaire can be completed in less than 30 seconds and is administered via pen-and-paper at the site visits at Week 2, Week 4, Week 8 and Week 12/ End of Study or Early Termination. Though data generated from the PGI-TS can be used for other purposes, its primary purpose is to support anchor-based analyses that will inform how researchers may interpret the meaning of change in the primary and secondary assessments.

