Clinician reported outcomes will be collected at study Visit 1, 2, 3, 4, 5 and 6. Patient-reported outcomes will be collected at study visit 2, 3, 4, 5, and 6 (with the exception of the PGI-C, PGI-TS and PGI-SE) which are not collected at Visit 1 or Visit 2). AEs and concomitant medications will be assessed throughout the treatment period. A urine pregnancy test is required at Visit 1, 2, 3, 4, 5 and 6 for all females of child-bearing potential and premenarchal.

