7.1.3 Supportive Efficacy Endpoints

The supportive efficacy endpoints are as follows:

- Proportion of Patients with an assessment of clear or almost clear and with at least a 2-grade improvement in IGA from Baseline, at Weeks 2, 4 and 8.
- Absolute change from Baseline in inflammatory and non-inflammatory lesion counts from Baseline to Week 2.
- PRE-FACE ASD: Mean absolute change in PRE-FACE ASD scores from Baseline to Weeks 2, 4, and 8.
- PRE-FACE AID: Mean absolute change in PRE-FACE AID scores from Baseline to Weeks 2, 4, and 8.
- Proportion of Patients in treatment relative to control who report at least “minimally improved” as measured by the PGI-C at Week 12.
- Patient Global Impress of Symptom Severity (PGI-S) at Week 12.
- Patient Global Impression of Treatment Satisfaction (PGI-TS) at Week 12.

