8.1.4 Adjustments for Covariates

Baseline lesion count will be a covariate for the primary efficacy endpoint for acne lesion counts. No other covariates are planned to be used in the analyses for this study.

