	E-BPO/E-ATRA 3%/0.1% Cream (N=xxx)	Vehicle Cream (N=xxx)	Treatment P-Value
Patient Global Impression of Treatment Satisfaction (PGI-TS) at Week 12			
0 - I am very satisfied	xx (xx.x%)	xx (xx.x%)	x.xxx ^b
1 - I am satisfied	xx (xx.x%)	xx (xx.x%)	
2 - I am neither satisfied nor dissatisfied	xx (xx.x%)	xx (xx.x%)	
3 - I am dissatisfied	xx (xx.x%)	xx (xx.x%)	
4 - I am very dissatisfied	xx (xx.x%)	xx (xx.x%)	
Patient Global Impression of Symptom Severity (PGI-S) at Week 12			
0 - None: no pimples, clear skin	xx (xx.x%)	xx (xx.x%)	x.xxx ^b
1 - Mild: very few pimples, almost clear skin	xx (xx.x%)	xx (xx.x%)	
2 - Moderate: some pimples	xx (xx.x%)	xx (xx.x%)	
3 - Severe: many pimples, almost no clear skin	xx (xx.x%)	xx (xx.x%)	
4 - Very severe: Large amount of pimples, no clear skin	xx (xx.x%)	xx (xx.x%)	
At Least “Minimally Improved” in PGI-C from Baseline to Week 12			
Success	xx.x%	xx.x%	x.xxx ^a
Failure	xx.x%	xx.x%	

^a P-value from a logistic regression with factors of treatment group and analysis center.

^b P-value from a cumulative logistic regression with factors of treatment group and analysis center.

Note: No imputation of missing values.

SOURCE: USERNAME\SPONSOR\PROJECT\JOBNAME (DATE, TIME)

{NOTE TO PROGRAMMER: ADJUST FOOTNOTE “d” IF FIRTH’S PENALIZED LIKELIHOOD IS NEEDED}

Table 14.2.11.1: Supportive Efficacy Analyses: Lesion Count and IGA
(Intent-to-Treat Population)
(Page 1 of 3)

	E-BPO/E-ATRA 3%/0.1% Cream (N=xxx)	Vehicle Cream (N=xxx)	Skewness P-Value	Treatment P-Value
At Least Two Grade Reduction from Baseline and Achieving Clear or Almost Clear at Week 8				
Success	xx.x%	xx.x%	N/A	x.xxx ^d
Failure	xx.x%	xx.x%		

^a Least squares means, standard deviations and treatment p-value from an analysis of covariance with factors of treatment and analysis center and the respective Baseline lesion count as a covariate. Negative least squares means values represent decrease from Baseline.

^b Skewness test, based on methods presented by J.H. Zar (1984), assessed for each imputed dataset.

^c P-value from a ranked analysis of covariance with factors of treatment and analysis center and the respective Baseline lesion count as a covariate.

^d P-value from a logistic regression with factors of treatment group and analysis center.

Note: Multiple imputation (MCMC) used to impute missing values.

SOURCE: USERNAME\SPONSOR\PROJECT\JOBNAME (DATE, TIME)

Table 14.2.11.1: Supportive Efficacy Analyses: Lesion Count and IGA
 (Intent-to-Treat Population)

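### Week 12 PGI-S is tested without the baseline PGI-S that the trial already collects: a modest, avoidable loss of precision on a supportive endpoint

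*SAP*

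**What the plan says.** SAP 7.1.3 lists the endpoint as "Patient Global Impress of Symptom Severity (PGI-S) at Week 12", a level and not a change. The test in SAP 8.7.4 is: "Inferential testing for PGI-S and PGI-TS at Week 12 will use a cumulative logistic regression with factors of treatment group and analysis center". Footnote b of Table 14.2.10.1 repeats it: "P-value from a cumulative logistic regression with factors of treatment group and analysis center". After naming baseline lesion count as the covariate for lesion counts, SAP 8.1.4 adds: "No other covariates are planned to be used in the analyses for this study". Missing PGI-S values are not imputed (SAP 8.7.4).

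The baseline value exists. The protocol synopsis schedules the "Patient Global Impression of Symptom Severity (PGI-S) at: Screening, Baseline, Weeks 2, 4, 8, and 12/ Early Termination", and the flow chart footnote in Protocol 12.10 says "Questionnaires are to be completed by all patients prior to any treatment related assessments". Table 14.2.15.1 tabulates baseline PGI-S by arm. PGI-TS, which shares the same sentence and model, is among the instruments "which are not collected at Visit 1 or Visit 2" (SAP 6.1).

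**The concern.** Most of the other efficacy outcomes tested between arms already use the baseline in some way. Lesion counts carry it as a covariate, IGA success and the PRE-FACE 4-point responders are defined against it, the PRE-FACE domain endpoints are changes from it, and PGI-C asks about change since the start of the study. PGI-TS has no baseline to use. PGI-S has one, measured on the same five-point scale, and it is used in neither the endpoint nor the model. The documents give no reason for the difference.

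Two things are at stake. Variation in self-rated severity at entry that persists to Week 12 stays in the error term. And randomization is stratified by site only (SAP 6.1.2), so nothing balances baseline PGI-S. If the baseline column of Table 14.2.15.1 turns out uneven, any adjustment made after unblinding would be post hoc.

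**Working it through.** **Inputs from the documents.** 280 and 140 patients (SAP 6.1.2); two-sided alpha 0.05 (SAP 8.1); model terms as in SAP 8.7.4.

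**Inputs not in the documents.** The correlation r between baseline and Week 12 PGI-S, the PGI-S effect, the category distribution and the missing rate. These are assumed, and r is varied.

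**1. The plan's own figure.** The plan gives no power for PGI-S. As a check of method, the inflammatory-lesion size in SAP 9 is reproduced. Vehicle n = (1 + 1/2) × (1.960 + 2.326)² × (10.0/4.5)² = 136.1, rounded up to 137. With 274 active this gives 411, as stated.

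**2. Analytic gain on a latent normal scale.** The standard error of the arm difference is √(1/280 + 1/140) = 0.1035 SD. An effect of 0.290 SD gives 80% unadjusted power, since 0.290/0.1035 = 2.80 = 1.96 + 0.84. Adjustment shrinks the residual SD to √(1 − r²), so adjusted power = Φ(2.80/√(1 − r²) − 1.96). The unadjusted test would need 420/(1 − r²) patients to match.

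| r | adjusted power | patients needed unadjusted |
|---|---|---|
| 0 | 80.0% | 420 |
| 0.2 | 81.6% | 438 |
| 0.3 | 83.6% | 462 |
| 0.4 | 86.4% | 500 |
| 0.5 | 89.9% | 560 |
| 0.7 | 97.5% | 824 |

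**3. Proportional-odds simulation with a five-category outcome.** Power is shown as unadjusted to adjusted.

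| Setting | r = 0 | r = 0.3 | r = 0.5 |
|---|---|---|---|
| 280 vs 140, shift 0.31 SD, no center term, 1,500 trials | 79.5% to 79.3% | 79.4% to 82.9% | 78.9% to 86.7% |
| 238 vs 119 (15% missing assumed), shift 0.315 SD, 1,500 trials | not run | 74.3% to 77.8% | 74.4% to 82.9% |
| shift 0.315 SD, analysis center in both models, 400 trials | no material loss | 75% to 79% | 72% to 81% |

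The Monte Carlo standard error is about 1 point for 1,500 trials and about 2 points for 400. The gain is about 4 points at r = 0.3 and 8 to 10 at r = 0.5, and including center does not remove it.

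**4. A larger effect.** The standardized effect for inflammatory lesions in SAP 9 is 4.5/10.0 = 0.45 SD. Take the second simulation row and scale (1.96 + z of the power) by 0.45/0.315 = 1.429.

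- Unadjusted: 2.61 × 1.429 − 1.96 = 1.77, about 96%.
- Adjusted, r = 0.3: 2.725 × 1.429 − 1.96 = 1.93, about 97%.
- Adjusted, r = 0.5: 2.910 × 1.429 − 1.96 = 2.20, about 98.6%.

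The gain is then about 1 to 2.5 points. Direct simulation with center at 0.45 SD also gave about 1 point, from about 97% unadjusted.

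**5. Chance imbalance.** Under the null, given a baseline difference of k standard errors, the unadjusted test statistic has mean r·k and variance 1 − r². For k = 2 the chance of |Z| > 1.96 is 8.1% at r = 0.3 and 13.4% at r = 0.5. For r = 0.5: (1.96 − 1.0)/0.866 = 1.108, upper tail 13.4%; the other tail is negligible.

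**6. Average type I error.** The simulated null at r = 0.5 rejected 5.9% unadjusted and 5.5% adjusted, with a standard error of about 0.6 points. Neither differs materially from 5%.

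**The case against.** The strongest case against is that this is a design preference. The planned comparison is randomized and holds its size, and no passage contradicts another. Protocol 17.4.4 sends discrete supportive variables to the IGA method, whose factors are treatment group and analysis center, and the SAP's model is the ordinal form of that. PGI-S is outside the gated sequence in SAP 8.1.8, has no power target, and is described in Protocol 12.20 as mainly an anchor for interpreting other measures. All of that stands, and it fixes the importance as low. It does not remove the point, because the baseline is already collected and its use costs no data.

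The objection about size also stands. The gain shrinks as the effect grows (step 4). Entry limited to IGA 3 or 4 may narrow the baseline PGI-S range and lower r.

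Three stronger readings are tempting and are not supported.

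- **That the planned test is biased or inflates alpha.** Step 6 shows it does not on average. The figures in step 5 are conditional on an unlucky allocation.
- **That adjustment would also correct dropout bias in this observed-case analysis.** Nothing in the documents says that dropout depends on baseline PGI-S, and the simulations above do not model it.
- **That this is the only between-arm test of the patient's overall view.** PGI-C at Week 12 is a global patient rating, referenced to study start and tested between arms. PRE-FACE items 1 and 5 are tested as reductions from Baseline within the gated sequence.

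Finally, scheduled for all patients does not mean that every form will be present.

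**Conclusion.** The point holds as a low-severity improvement. SAP 8.7.4, SAP 8.1.4 and footnote b of Table 14.2.10.1 together leave baseline PGI-S out of the only model for Week 12 PGI-S. The loss is in precision and in protection against chance imbalance. Its direction is certain for any nonzero correlation; its size is not, because it rests on an assumed r and an assumed effect. The 8-to-10-point figure needs both r near 0.5 and unadjusted power of about 75-80%. With a larger effect or a weak correlation the gain may be too small to notice. No primary or secondary conclusion depends on it.

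**What to change.** Before unblinding, make these changes for Week 12 PGI-S:

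- Add baseline PGI-S to the cumulative logistic model in SAP 8.7.4 and in footnote b of Table 14.2.10.1.
- Fix its coding in advance: either a linear score, or categories merged by a rule set on blinded data, for example merging any level with fewer than 5% of patients into its neighbor.
- If the Baseline form is missing, use the Screening PGI-S. This follows the SAP 8.1.2 definition, which takes the latest available value before treatment starts. Protocol 12.20 says "The PGI-S will be administered at study visits 2-6, including Screening, Baseline" and the flow chart marks PGI-S at Visit 1, while SAP 6.1 lists patient-reported outcomes only from Visit 2, so confirm that Screening forms are collected.
- Label the odds ratio as conditional on baseline PGI-S. It will usually lie further from 1 than the unadjusted one: in simulation at r = 0.5 the log odds ratio was −0.61 against −0.53.
- Amend the last sentence of SAP 8.1.4 to allow this covariate.
- Leave PGI-TS unchanged, since it has no baseline.

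The cost is one model term and a few SAP sentences, with no new data. The SAP Preface allows updates until the blind is broken. At r = 0 the simulations show no material loss from the extra term.
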